### **Opi-Prim**

#### ***Trial Design***

Pragmatic controlled before-and-after study

**Trial No:** *Trial will be registered after feasibility study at  
clinicaltrials.gov*


The evidence for prescribing opioids to patients suffering from chronic non-cancer pain is weak, and using opioids in these circumstances is questionable. Swedish primary health care is responsible for about one-third of all first-time opioid prescriptions and has the highest rate of prescription renewals for opioids. The decision for long-term opioid therapy (LTOT) should rest on an accurate pain analysis and should result in an individualized assessment where the risks of LTOT are set against the impact on quality of life that living with long-term pain entails. Multi-professional interventions and a person-centered approach are recommended for chronic non-cancer pain. Although pharmacists in primary health care have been established internationally with successful examples related to LTOT, their role in Swedish primary care and the management of chronic non-cancer pain remains to be studied. Currently, it is unclear which interventions are effective in reducing inappropriate LTOT and which alternative interventions are suitable for patients who are currently receiving LTOT. The involvement of a care manager in the patient's care has shown promising results regarding quality of care for other long-term conditions, for example depression. In Region Uppsala, clinical pharmacists have recently been employed in primary health care, but it is unclear what their tasks and responsibilities are and how to best make use of their competence. It is therefore relevant and justified to investigate a new person-centered team-based approach including care manager and pharmacist to optimize the management of pain in patients with chronic non-cancer pain in Swedish primary care. This project aims to reduce inappropriate LTOT and optimize pain management in patients with LTOT for chronic non-cancer pain in primary care through a new person-centered and team-based approach.

Primary objective:
To investigate the effects of a new person-centred and team-based approach on pain interference in patients with LTOT for chronic non-cancer pain in primary care
Secondary objectives:
To investigate the effects of a new person-centred and team-based approach in patients with LTOT for chronic non-cancer pain in primary care on secondary endpoints and to perform a process evaluation alongside the trial, including a feasibility study.
Primary endpoint:
Pain interference measured after 3, 6, and 12 months
Secondary endpoints:
Pain intensity, symptoms of depression, symptoms of anxiety, patient satisfaction, health-related quality of life, opioid use (morphine equivalents) and symptoms of withdrawal. All secondary endpoints will be measured after 3, 6, and 12 months.
Trial design and setting:

This study is a controlled before-and-after study that has been designed, and will be reported, according to the CONSORT guidelines. Participation will be during 52 weeks (12 months).
 
This study will be conducted at eight healthcare centres in Region Uppsala. At four of the healthcare centres, a new person-centred team-based treatment model including pharmacists (intervention) will be implemented. Prerequisites for these healthcare centres are the accessibility of at least one person of each healthcare profession: pharmacist, general practitioner (GP), psychologist (or social worker) and physiotherapist, where one of these (or a rehabilitation coordinator or a nurse) takes the role of care manager. Healthcare personnel will receive special training in managing patients with chronic pain before the study. In addition, four control healthcare centres without a pharmacist will be matched with the intervention healthcare centres according to geographic area (urban, suburban, rural), socioeconomical setting and the size of the centres (number of listed patients). No specific efforts of implementation will be made in these control centres.
 
Prior to the full trial, a feasibility study will be conducted at one intervention centre and one control centre with 12 weeks follow-up per participant.

**Trial population:**

Eligible patients in the study are adult (>18 years) patients with their main healthcare contact at one of the healthcare centres included in the study, who have received long-term opioid therapy (> 90 days) for chronic pain prescribed by a GP during the recent 12 months, according to the primary healthcare quality indicator "Lm12alla".

**Number of subjects:**

Sample size calculations resulted in at least 55 participants per treatment group (110 in total) needed to measure a clinically relevant difference in the primary outcome. For the feasibility study, 5-10 participants per treatment group will be included.

**Inclusion criteria:**

Adult (>18 years) patient, main health care contact at one of the health care centres included in the study, received more than the equivalent of 90 days or more prescription of opioids for chronic pain made by GP during the recent 12 months, according to the primary healthcare quality indicator: "Lm12alla".

**Exclusion criteria:**

No current opioid use, been referred to a pain clinic or something similar during the last 6 months, is not able to speak Swedish, and is not able to provide informed consent.

**Intervention:**

Patients with pain > 3 months and treatment with opioids at the intervention healthcare centres who have agreed to participate will start their inclusion in the person-centred team-based treatment immediately at the index appointment. The intervention will be performed by healthcare personnel (GP, clinical pharmacist, physiotherapist and psychologist) who receive two half-days of training in person-centered care and managing patients diagnosed with chronic pain, before the study starts. The intervention will then consist of three phases.

*Phase 1 (investigation and assessment, week 1-3):*

- A medication review focusing on pain, sleep and depression/anxiety disorders according to the Swedish National Board of Social Affairs and Health HSLF-FS 2017:37 by a pharmacist.
- A thorough pain analysis by a GP according to existing guidelines including duration of pain, pain localization and pain mechanisms.
- A visit to a physiotherapist for evaluation and assessment of possible treatment regarding physical exercise/physical activities and related treatments.
- A visit to a psychologist for diagnostics and treatments regarding psychological and social factors.
- A visit to a care manager

*Phase 2 (treatment plan, week 3-4):*

- An appointment with all healthcare personnel involved in Phase 1 including the patient where an individualized rehabilitation plan is made based on the biopsychosocial model of pain and in accordance with the Swedish Medical Products Agency's treatment recommendations.

*Phase 3 (treatment and follow-up, week 4-24):*

- Implementation of the individualized rehabilitation plan.
- Frequent follow-up contacts (1 per 1-3 weeks) by phone with an established contact person, i.e. care manager (pharmacist, physiotherapist, psychologist, rehabilitation coordinator or nurse).  
An appointment with all healthcare personnel involved in the rehabilitation plan, 3-4 months after the start of phase 2 to update the plan.

**Control:** Usual care at one of the control healthcare centres.

**Ethical considerations:**

Ethical considerations have been made. All participants will provide written informed consent prior to trial participation. The feasibility study of this trial has received ethical approval from the Swedish Ethical Review Authority (registration number 2023-00313-01, date: 2023-04-23). Ethical approval will be sought for the final version of the trial protocol before the full trial can be conducted.

**Trial period:**

Feasibility study: Q3 2023 – Q1 2024

Trial: Q2 2024 - Q4 2026

## 2 LIST OF ABBREVIATIONS

*List the abbreviations used in the protocol. At first appearance in the text, the abbreviated term should be spelled out and the abbreviation should be indicated in parentheses. Define the specialised or unusual terms used in the protocol.*

AE	Adverse Event
ASR	Annual Safety Report ( replacing the previous DSUR )
CRF	Case Report Form
CTR	EU Regulation 536/2014, also called CTR, Clinical Trials Regulation
GCP	Good Clinical Practice
IB	Investigator's Brochure
ICH	International Council for Harmonisation
SAE	Serious Adverse Event
SmPC	Summary of Product Characteristics
SUSAR	Suspected Unexpected Serious Adverse Reaction

## 3

## BACKGROUND INFORMATION

Opioids are crucial for treatment of severe acute pain, during surgery, after trauma or when treating cancer related pain(1,2). However, the evidence for good pain relief for patients suffering from chronic non-cancer-pain is weak and using opioids during these circumstances is questionable(1,3,4). Although the opioid-prescription in Sweden is not anywhere near that in North America, there has in Sweden in recent years, been a shift from weak opioids (e.g. tramadol) to stronger opioids (e.g. oxycodone)(2,2,5). Furthermore, primary health care in Sweden is responsible for about one third of all first-time opioid prescriptions and has the highest rate of prescription renewals for opioids(2). There are indications of patients in primary health care, for which opioid prescriptions are renewed even though the indication for opioid treatment is doubtful, where a plan for the dose and duration of opioid prescription is missing and with multiple prescribers for their opioids.

The decision for long-term opioid therapy (LTOT) should rest on an accurate pain analysis based on the biopsychosocial model and should result in an individualized assessment where risks of LTOT are set against the impact on quality of life the living with long-term pain entails(3–11). Multi-professional and person-centred interventions are recommended for chronic non-cancer pain(7). However, opioid therapy may reduce patient motivation for such interventions(12–14). Currently, it is unclear which interventions are effective in reducing inappropriate LTOT and which alternative interventions are suitable for patients that are currently receiving LTOT(15). International research shows that active tapering of opioids with team-based interventions can be implemented successfully (8,12,16), but forms for implementing this in outpatient care in Sweden need to be developed and evaluated.

Clinical pharmacists in primary health care have been established internationally, for example in the UK, but are so far uncommon in the Swedish primary health care system(17). There are many international examples of successful collaboration with clinical pharmacists to reduce LTOT among patients suffering from chronic pain but their role in Swedish primary care and the management of chronic non-cancer pain remains to be studied(17). In Region Uppsala, clinical pharmacists have recently been employed in primary health care, but it is unclear what their tasks and responsibilities are and how to best make use of their competence. This provides an opportunity to investigate their potential role in reducing inappropriate LTOT in Swedish primary health care.

Primary healthcare providers in Region Uppsala are referred to the document “Pain-chronic pain, systematic investigation Primary health care” (18)which is based on national assessment and treatment guidelines.

How these guidelines are implemented in primary health care is unclear. Preparatory studies to this project show a lack of routines for person-centred and team-based work as well as lack of routines of opioid tapering, and suggests that patients treated with opioids appear to be excluded from multi-professional care. The GPs in our preparatory interview study signalled that patients treated with opioids would need

more extensive care to taper their medication. The pharmacists in the focus group interviews reported a desire to be more involved in the clinical work in general and opioid treatment in particular in patients with chronic pain. Other healthcare personnel at the healthcare centres requested more insight into each other's work and improved teamwork. It is therefore relevant and justified to investigate a new person-centred team-based approach that includes pharmacist involvement to optimize the management of pain in patients with chronic non-cancer pain in Swedish primary care.

## **5 TRIAL OBJECTIVES**

The overall aim of this project is to reduce inappropriate LTOT and to optimize pain management in patients with LTOT for chronic non-cancer pain in primary care through a new person-centred and team-based approach.

### **5.1 PRIMARY OBJECTIVES**

The primary objective is to investigate the effects of a new person-centred and team-based approach on pain interference in patients with LTOT for chronic non-cancer pain in primary care.

### **5.2 SECONDARY OBJECTIVES**

The secondary objective is to investigate the effects of a new person-centred and team-based approach in patients with LTOT for chronic non-cancer pain in primary care on secondary endpoints and to perform a process evaluation alongside the trial, including exploring the feasibility of the study design.

## **6 TRIAL DESIGN AND SETTING**

### **6.1 TRIAL OUTLINE**

The trial is a controlled before-and-after study that has been designed, and will be reported, according to the applicable CONSORT guidelines (19). No randomization or blinding will be involved. A feasibility study will be conducted prior to the full trial.

### **6.2 SETTING AND SITE SELECTION**

This study will be conducted at eight healthcare centres in Region Uppsala, NVH. At four of the healthcare centres a new person-centred team-based treatment model including pharmacists (intervention) will be implemented. Basic conditions for these healthcare centres are the accessibility of at least one person of each healthcare profession: pharmacist, GP, psychologist and physiotherapist, where one of these (or a rehabilitation coordinator or a nurse) takes the role of care manager. Healthcare personnel will receive special training in person-centered care and managing patients diagnosed with chronic pain before the study. In addition, four control healthcare centres without a pharmacist will be matched with the intervention healthcare centres

according to according to geographic area (urban, suburban, or rural) and the size of the centres (number of listed patients). No specific efforts for implementation will be made in these control centres.

Patients being participants at the intervention health care centres will start their inclusion in the new person-centred team-based treatment immediately at the index appointment and up to 24 weeks. Participants at the control centres will receive usual care.

### 6.3 STAFF TRAINING AND IMPLEMENTATION

All personnel involved in the study (GPs, physiotherapists, psychologists (or social workers), pharmacists including the care manager) will participate in two half day-sessions of training. In addition to the two half-day sessions, the care managers (i.e. one in the team above, a rehabilitation coordinator or a nurse) will receive additionally two hours of training in providing person-centred and team-based care. The education focuses on optimized diagnostics and treatment of pain according to the biopsychosocial model including pharmacological aspects. The training includes interactive and case-based lectures on chronic pain, opioids, person-centred care and teamwork. The training will be held locally at each healthcare centre and be arranged by persons from the research group in collaboration with a psychologist and a physiotherapist from the Pain Clinic, Uppsala Academic Hospital. Further, the training will include information about the study. To ensure an adequate pain analysis the personnel involved will also receive instructions about how to document relevant findings in the patients' electronic health recordings. To avoid duplication of work and overlaps at the various care visits, checklists will be created for each profession respectively, to result in coordinated documentation.

It is the responsibility of the investigators to ensure that all personnel involved in the trial are fully informed of all relevant aspects of the trial, including detailed knowledge of and training in all procedures to be followed.

## 7 SELECTION AND WITHDRAWAL OF SUBJECTS

### 7.1 SUBJECT INCLUSION CRITERIA

Eligible patients in the study are adult (>18 years) patients with their main healthcare contact at one of the healthcare centres included in the study who have received the equivalent of 90 days or more prescription of opioids for chronic pain made by GP during the recent 12 months, according to the primary healthcare quality indicator "Lm12alla" (20), and provided written informed consent to participate.

### 7.2 SUBJECT EXCLUSION CRITERIA

Patients will be excluded if:

- They have been referred to a pain clinic (either at hospital or multimodal rehabilitation in primary care) within the last 6 months

- They have no current opioid use, severe cognitive dysfunction, e.g., suicidal ideation, psychotic symptoms, or dementia, that prevents informed consent.
- They use their opioids for cancer pain

### 7.3 WITHDRAWAL OF SUBJECTS

Subjects have the right to withdraw from the trial at any time without prejudice to future treatment. In addition, the subject may be withdrawn at the investigator's discretion at any time if it is in the subject's best interest. In the event that the subject drops out or withdraws from the trial, the reason for study discontinuation will be recorded in the CRF.

Reasonable efforts should be made to contact any subject lost to follow-up after end of treatment in order to complete assessments and retrieve any outstanding data.

Specific criteria for withdrawal are:

- Subject's decision
- Investigator's discretion
- Subject lost to follow-up/non-attendance
- Intercurrent illness

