#### 8.2 PHASE 3 (TREATMENT AND FOLLOW-UP, WEEK 4-24):

- Implementation of the individualized rehabilitation plan.
- Frequent follow-up contacts (1 per 1-3 weeks) by phone with an established care manager, i.e. contact person (one of the team staff or a rehabilitation coordinator or a nurse) with a person-centred approach. The care manager's responsibility will be to ensure that health services meet their commitments in the care plan and to serve as a main point of contact between participants and health care.
- An appointment with all health care personnel involved in the rehabilitation plan, 3-4 months after the start of phase 2 to update the plan.

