### 12.2 STATISTICAL ANALYSIS

Primarily, statistical analyses will be conducted based on intention-to-treat (ITT) principle. Patient characteristics will be presented descriptively per treatment group. The average value of pain interference and quality of life in accordance with BPI-SF will be calculated and analyzed separately per treatment group. The difference between the intervention group and the control group will be analysed through regression analysis including the ability to adjust for base line data and other covariates. ANOVA for repeated measurements will be used to analyse the average differences between the two groups until 12 months. The number of dropouts will be reported and analysed descriptively. All randomized study subjects completing the whole study period (complete cases) will be analyzed Per Protocol. For a specific analysis, study subjects with missing data on any of the variables in the model will be excluded from the analysis. Analyses of this population is seen as sensitivity analysis to investigate whether conclusions are sensitive to assumptions regarding the pattern of missing data. All analyses will be described in a prespecified statistical analysis plan (SAP). Significance tests will be two-tailed and a p-value less than 0.5 will be interpreted as significant. All statistical analyses are carried out in an SPSS, SAS or R. The process evaluation is analysed descriptively as well as through a qualitative thematic analysis.

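### Section 7.3 lists reasons for leaving the trial without separating a stop of the intervention from the end of outcome collection, which undermines the intention-to-treat analysis

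*Protocol*

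**What the plan says.** Protocol section 7.3 gives four specific criteria for withdrawal: the subject's decision, the investigator's discretion, "Subject lost to follow-up/non-attendance" and "Intercurrent illness". On the second it adds that "the subject may be withdrawn at the investigator's discretion at any time if it is in the subject's best interest". What is being left is the trial itself and not only the intervention: "In the event that the subject drops out or withdraws from the trial, the reason for study discontinuation will be recorded in the CRF". Non-attendance is not defined, and intercurrent illness carries no qualifier.

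On retrieving data the section has one sentence: "Reasonable efforts should be made to contact any subject lost to follow-up after end of treatment in order to complete assessments".

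Section 12.2 states: "Primarily, statistical analyses will be conducted based on intention-to-treat (ITT) principle". Section 12.2.1 puts every eligible subject into the analyses. Section 9.1 collects the primary outcome through a digital link, with a telephone reminder if data are missing. Section 12.3 sizes the trial on the difference in change at 12 months.

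The arms differ in what the protocol asks patients to attend. In the intervention arm, section 8 schedules pharmacist, GP, physiotherapist and psychologist contacts, two team appointments, and "Frequent follow-up contacts (1 per 1-3 weeks) by phone with an established care manager" up to week 24. Under section 8.3, controls receive usual care.

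**The concern.** An intention-to-treat comparison needs outcomes from patients who stop attending, fall ill or are taken out of the programme. Section 7.3 names these situations as reasons to leave the trial and does not say that the questionnaires go on afterwards. A site that follows it literally could stop contacting a patient in week 6 and so lose the 3, 6 and 12 month values. The statistical analysis plan can say how missing values are handled, but it cannot restore questionnaires that were never sent.

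The loss could also be uneven. Only intervention patients have a protocol programme to miss, and section 6.1 says that there is no blinding. Section 13.1 notes that opioid reduction may bring temporary abstinence symptoms and increased pain, so withdrawal in the patient's interest could be related to the primary outcome. At stake is bias in the 12-month difference.

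**Working it through.** **1. The plan's own figure.** Inputs from sections 12.2 and 12.3: difference 1.0, SD of change 1.43, power 90%, two-sided 5%, 1:1, 20% dropout, 46 per group raised to 55.
- Normal approximation: 2 × (1.960 + 1.282)² × 1.43² / 1.0² ≈ 43 per group.
- t-test: 43.96, so 44 per group. The stated 46 is two patients higher.
- 55 less 20% is 55 × 0.8 = 44 per group, so the target of 55 delivers the stated power by the t-test.

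**2. Who is covered after withdrawal.** This sets the criteria in 7.3 against its retrieval sentence.

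| Reason for withdrawal | Retrieval effort stated in 7.3? |
|---|---|
| Lost to follow-up after end of treatment | Yes |
| Lost to follow-up or non-attending during treatment | Unclear: only if the sentence means that contact is made after treatment ends |
| Intercurrent illness | No |
| Investigator's discretion | No |

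**3. How the arms are exposed, if non-attendance means missed care visits.** Calls run from week 4 to week 24, which is 20 weeks. At one per 3 weeks that is 20/3 ≈ 7 calls; at one per week it is 20. The Phase 1 visits and two team appointments come on top. After the index appointment, controls have no protocol care visit to miss.

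**4. Effect on power.** The protocol gives dropout only overall, so the split by arm is assumed. Power by t-test for a difference of 1.0:

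| Followed, intervention / control | Loss, intervention / control | Power |
|---|---|---|
| 44 / 44 | 20% / 20% | 90% |
| 38 / 50 | 31% / 9% | 90% |
| 33 / 50 | 40% / 9% | 87% |
| 27 / 50 | 51% / 9% | 82% |

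At a similar total loss, imbalance costs almost no power. The issue is bias.

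**5. Size of a possible bias.** Let a share d of one arm be lost, and let their mean change be g points worse than that of the patients retained. The observed arm mean is then too favourable by d × g. Neither d nor g is in the documents.
- d = 10%, g = 1.0: 0.1 points.
- d = 20%, g = 1.0: 0.2 points.
- d = 30%, g = 1.0: 0.3 points.
- Wider range, d = 10% to 40% and g = 0.5 to 1.5: 0.05 to 0.60 points.

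**6. What that would do to a 5% two-sided test.** SE = 1.43 × √(2/44) = 0.305. With no true effect, a bias of 0.1, 0.2 or 0.3 gives a rejection rate of 6.2%, 10.1% or 16.6% (normal approximation). These rates assume no offsetting loss among controls and no correction through baseline adjustment.

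**The case against.** A reader might infer that section 7.3 contradicts the intention-to-treat analysis outright. The text does not support that. Nothing says that withdrawn subjects leave the analysis set or that their data are discarded. Section 12.2.1 includes all eligible subjects, and section 12.2 gives complete cases a separate per-protocol analysis, which implies that the main set also holds non-completers. This part of the objection stands: the fault lies in data collection, not in the definition of the set.

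A reader might also infer that the rule will remove intervention patients selectively. That goes too far. The criteria apply to both arms, intercurrent illness can occur in either, and investigator withdrawal is optional and tied to the patient's interest. Non-attendance is paired with loss to follow-up and may mean missed assessments. Sections 10.1 and 10.2 treat incomplete delivery as something to measure and do not make it a ground for removal. Only the statement that the loss may be uneven can be supported, and only if non-attendance means care visits.

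The direction of any bias is likewise open, since section 13.1 leaves room for patients who stay in the programme to have more pain for a time.

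Finally, section 9.1 names no exception to the digital link and reminder call, so collection might continue in practice. That is possible, but 7.3 speaks of leaving the trial, and no sentence tells a site to go on contacting a patient withdrawn for illness or at the investigator's discretion.

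**Conclusion.** The point holds in a limited form. Section 7.3 does not separate stopping the intervention from leaving follow-up, and its retrieval sentence does not reach every listed reason. That undermines the intention-to-treat analysis, because 12-month outcomes may be missing for patients withdrawn earlier. Uneven loss between arms is a plausible risk that depends on an undefined term; it is not a stated consequence. The 0.1 to 0.3 points (10% to 30% of the 1.0-point target) and the rejection rates are illustrations that rest on an assumed one-arm loss and an assumed 1.0-point gap. The documents establish neither, nor the sign. A correction is worth making because the gap concerns data collection, which a later analysis plan cannot repair.

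**What to change.** In section 7.3:
- define non-attendance, saying whether it refers to care visits or outcome assessments;
- separate stopping the intervention from leaving follow-up;
- state that, after non-attendance, intercurrent illness or an investigator's decision, the 3, 6 and 12 month questionnaires continue through the digital link and reminder call, and the subject stays in the intention-to-treat set, unless the subject withdraws consent to follow-up.

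The clinical reasons for stopping treatment are left as they are.

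The cost is a few lines of protocol text, a line in the consent information so that patients know the questionnaires continue, and a few more reminders. Outcome collection does not depend on care visits. Section 10.1 already foresees a protocol update after the feasibility study, and the change can be made then.
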